11.3.3 Pharmacokinetic populations

The PK population of the parallel-arms period will consist of all randomized patients who receive at least at least 1 dose or part of a dose of IMP and had at least one evaluable blood sample for PK during this period. All patients will be analyzed according to the auto-injector device that they actually used.

The PK population of the single-arm period will consist of all randomized patients who receive at least 1 dose or part of a dose of IMP and had at least one evaluable blood sample for PK during this period.

These PK populations will be used for the analyses of alirocumab concentrations and PCSK9 concentrations.

11.3.4 Anti-alirocumab antibody population

The anti-alirocumab antibody population of the parallel-arm period will consist of all randomized patients who receive at least 1 dose or part of a dose of IMP during this period (safety population) with an available ADA sample at baseline and at least one post-baseline available ADA sample during this period.

The anti-alirocumab antibody population of the single-arm period will consist of all randomized patients who receive at least 1 dose or part of a dose of IMP during this period (safety population) with an available ADA sample at baseline and at least one post-baseline available ADA sample during this period.

11.4 STATISTICAL METHODS

Unless otherwise specified, analyses will be performed by auto-injector device group in the parallel-arms period and overall in the single-arm period.

The baseline value is defined as the last available value obtained up to the date and time of the first IMP administration.

11.4.1 Extent of study treatment exposure and compliance

The extent of study treatment exposure and compliance will be assessed and summarized by actual auto-injector device used within the safety population for each study period.

11.4.1.1 Extent of investigational medicinal product exposure

No duration of IMP exposure will be calculated for the parallel-arms period since patients will receive only one injection during this period. The proportion of patients having received the first injection will be summarized.

The duration of IMP exposure for the single-arm period is defined as: last IMP injection date - first IMP injection date during this period + 28 days (regardless of unplanned intermittent discontinuations). The number of injections received during the single-arm period will also be summarized.

11.4.1.2 Compliance

No treatment compliance to the IMP will be calculated for the parallel-arms period since patients will receive only one injection during this period.

Treatment compliance to the IMP for the single-arm period will be assessed using the mean injection frequency, defined for each patient, as the average number of days between 2 consecutive injections, that is: (last injection date – first injection date during this period)/(number of injections - 1) for patients receiving at least 2 injections during this period.

11.4.2 Analyses of primary endpoint

The primary endpoint (ie, number (%)) and types of SYDNEY-associated PTCs related to the unsupervised injections [Section 9.1]) will be described on the safety population for the single arm period. The number and % of PTCs will be provided with the 95% CI using Wilson score method. If applicable, the number of PTCs per patient will be described. In addition the type of PTCs will be described.

11.4.3 Analyses of secondary efficacy endpoints

All secondary device-related endpoints (Section 9.2.1) will be analyzed on the safety population using descriptive statistics. In addition, 95% CI for the number of PTCs, number and % of patients with any PTCs will be provided using Wilson score method.

11.4.4 Analyses of safety data

Safety data will be presented on the safety population of the parallel-arm period and of the single-arm period. Treatment-emergent adverse events (TEAEs), treatment-emergent SAEs, treatment-emergent AESIs, and TEAEs leading to treatment discontinuation, will be summarized based on the Medical Dictionary for Regulatory Activities (MedDRA) coding of verbatim terms reported by investigators (Section 9.2.5).

All safety analyses will be performed using the following common rules:

- The observation period to be used for the safety population is the TEAE period. The TEAE period is defined
 - For the parallel-arms period as the time from the first IMP injection to the day before the second IMP injection (for patients entering into the single arm period period) or to 70 days after the first IMP injection, whichever comes first
 - For the single-arm period as the time from the first IMP injection received in the single arm period to 70 days after the last IMP injection.

The following definitions will be applied to laboratory parameters, and vital signs:

- The potentially clinically significant abnormality (PCSA) values are defined as abnormal values considered medically important by the Sponsor according to predefined criteria/thresholds based on literature review and defined by the Sponsor for clinical laboratory tests, and vital signs.
- Potentially clinically significant abnormality criteria will determine which patients had at least 1 PCSA during the TEAE period, taking into account all evaluations performed, including unscheduled or repeated evaluations. The number of all such patients will be the numerator for the on-treatment PCSA percentage.

- Treatment period: the treatment period used for quantitative analysis is defined:
 - For the parallel-arms period as the time from the first IMP injection to 35 days after this injection or to the day before the second IMP injection (for patients entering into the single arm period period) whichever comes first.
 - For the single-arm period as the time from the first IMP injection received in the single arm period to 35 days after the last IMP injection.

11.4.4.1 Analysis of the adverse event data

The analyses of AEs will focus on TEAEs. Treatment-emergent AEs are defined as any AEs that are newly developed or worsened or that become serious during the TEAE period.

Treatment-emergent AE incidence tables will present the number (%) of patients experiencing at least 1 TEAE by system organ class (SOC) (sorted by internationally agreed order), high-level group term (HLGT), high-level term (HLT) and preferred term (PT) sorted in alphabetical order. Multiple occurrences of the same event in the same patient will be counted only once in the tables within a treatment phase. The denominator for computation of percentages is the safety population within each auto-injector device group.

Adverse event incidence table will be provided for all types of TEAEs: all TEAEs, all treatment-emergent AESI (defined with a PT or a prespecified grouping), all treatment-emergent SAEs and all TEAEs leading to permanent treatment discontinuation.

Death: The following summaries will be provided:

- Number (%) of patients who died by study period (TEAE, on-study) and reasons for death summarized on the safety population
- Death in nonrandomized patients or randomized and not treated patients
- TEAE leading to death (death as an outcome on the Adverse Event CRF page as reported by the Investigator) by primary SOC, HLGT, HLT and PT showing number (%) of patients sorted by internationally agreed order of SOC and alphabetic order of HLGT, HLT, and PT.

11.4.4.2 Analysis of the laboratory data

For laboratory data, including the incidence of PCSAs, actual values and change from baseline will be summarized by treatment group.

The number and percentage of patients with at least 1 PCSA at any time during the TEAE period will be summarized for each laboratory parameter. Shift tables showing changes with respect to the baseline status will be provided.

The summary statistics (including number, mean, median, standard deviation, minimum, and maximum) of all laboratory variables will be calculated for each visit (baseline, each post-baseline time point, endpoint) by auto-injector device group.

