--	--

	
Safety and tolerability
 
The safety analysis will be based on the review of the individual data and descriptive statistics.
 
Adverse events will be classified using Medical Dictionary for Regulatory Activities (MedDRA) system organ class and preferred term. The number of treatment-emergent adverse events (TEAEs) will be tabulated by auto-injector device, as well as treatment-emergent AESIs (including in particular local injection site reactions LISR), treatment-emergent SAEs, TEAEs leading to permanent treatment discontinuation.
 
For vital signs and laboratory parameters, the number of patients with abnormalities and/or potentially clinically significant abnormalities (PCSAs) will be summarized by auto-injector device.

DURATION OF STUDY PERIOD (per patient)	
Total study duration (per patient) is expected to be up to 18 weeks:
 
• Up to 2 weeks of screening period• 16 weeks of study treatment period (auto-injector device assessment phase).

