1 FLOW CHARTS

1.1 GRAPHICAL STUDY DESIGN

1.2 STUDY FLOW CHART

Phase	Screening	Treatment Phase										
Day ^a	D-14 to D-1	D1	D8 (±1)	D15 (±1)	D22 (±1)	D29 (±3)	D57 (±3)	D85 (±3) EOT	D92 (±1)	D99 (±1)	D106 (±1)	D113 (±3) EOS
Week	Wk-2 to Wk 0	Wk 0	Wk 1	Wk 2	Wk 3	Wk 4	Wk 8	Wk 12	Wk 13	Wk 14	Wk 15	Wk 16
Visit (visit number)	1	2	3 ^b	4 ^b	5 ^b	6 ^b	7 ^b	8	9 ^b	10 ^b	11 ^b	12
Place where visits may occur	On-site	On-site	On-site or home	On-site	On-site or home	On-site or home	On-site or home	On-site				
Informed consent	X											
Inclusion/exclusion criteria	X	X										
Patient demography	X											
Medical/surgical history	X											
Prior/concomitant medications	X	X	X	X	X	X	X	X	X	X	X	X
Randomization		X										
Study treatment administration^c												
Training injection with both devices (prior to randomization) ^d		X										
alirocumab SC injection using SYDNEY		X ^e				X ^f	X ^f	X ^e				
alirocumab SC injection using AI		X ^e										
Dispense/Complete/Review patient diary		X				X ^f	X ^f	X				
Contact IRT		X				X	X	X				X
Dispense alirocumab device		X				X ^f	X ^f	X				
Collect devices post-injection		X					X	X				
Treatment compliance		X					X	X ^g				
End user data recording												
Product Technical Complaints		X				X ^f	X ^f	X				
Patient perspective questionnaire ^h								X				
Injection-Treatment Acceptance Questionnaire (I-TAQ®) ⁱ								X				
Injection Experience questionnaire ^j		X				X	X	X				

Phase	Screening	Treatment Phase										
Day ^a	D-14 to D-1	D1	D8 (±1)	D15 (±1)	D22 (±1)	D29 (±3)	D57 (±3)	D85 (±3) EOT	D92 (±1)	D99 (±1)	D106 (±1)	D113 (±3) EOS
Week	Wk-2 to Wk 0	Wk 0	Wk 1	Wk 2	Wk 3	Wk 4	Wk 8	Wk 12	Wk 13	Wk 14	Wk 15	Wk 16
Visit (visit number)	1	2	3 ^b	4 ^b	5 ^b	6 ^b	7 ^b	8	9 ^b	10 ^b	11 ^b	12
Place where visits may occur	On-site	On-site	On-site or home	On-site	On-site or home	On-site or home	On-site or home	On-site				
Safety												
Physical examination	X											X
Height	X											
Body weight	X											X
Vital signs (Blood Pressure ^k , Heart Rate)	X	X				X	X	X				X
Hematology ^m , biochemistry ^m (including fasting plasma glucose)	X	X										X
Creatine phosphokinase	X	X				X	X	X				X
Liver function panel (ALT, AST, ALP & total bilirubin ^l)	X	X				X	X	X				X
Serum pregnancy test (if applicable)	X											
Urine pregnancy test (if applicable)		X										X
Adverse event collection	X	X	X	X	X	X	X	X	X	X	X	X
Pharmacokinetics												
alirocumab pharmacokinetic samples ⁿ		X	X	X	X	X	X	X	X	X	X	X

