9.2.5.2 Laboratory safety variables

The clinical laboratory data consist of blood analysis including the following:

- Hematology: red blood cell count, hematocrit, hemoglobin, white blood cell count with differential count (neutrophils, eosinophils, basophils, monocytes, and lymphocytes), platelets.
- Biochemistry: sodium, potassium, chloride, calcium, plasma glucose, urea nitrogen, creatinine, albumin, total proteins, gamma-glutamyl transferase (γ GT).
- Liver function panel: aspartate aminotransferase (AST), Alanine aminotransferase (ALT), alkaline phosphatase (ALP), and total bilirubin (and, in case of values above the normal range, differentiation in conjugated and non-conjugated bilirubin).
- Creatine phosphokinase (CPK).
- Urine and serum (beta-human chorionic gonadotropin [β -HCG]) pregnancy test for women of child bearing potential (WOCBP) only.

Clinical laboratory values will be analyzed after conversion into standard international units. International units will be used in all listings and tables.

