9.3 SAMPLED BLOOD VOLUME

The volume of blood sampled in the study is shown in [Table 8](#).

Table 8 - Sampled blood volume

Type	Volume per sample	Sample number	Total
Hematology	2 mL	3	6 mL
Biochemistry	2 mL	3	6 mL
Creatine phosphokinase	2 mL	6	12 mL
Liver function panel	1 mL	6	6 mL
Pharmacodynamics	3 mL	6	18 mL
β-HCG (if applicable)	5 mL	1	5 mL
Pharmacokinetics alirocumab	5 mL	11	55 mL
Anti-alirocumab antibody	5mL	3	15 mL
Total if male or female post menopausal			118 mL
Total if WOCBP			123 mL

Abbreviations: β-HCG: beta-human chorionic gonadotropin, WOCBP: Women of childbearing potential

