2.4.4.2.5 Safety variables

The summary of safety results will be presented separately for the parallel-arm and single-arm periods. The parallel-arm period will be presented by treatment group and the single-arm period will be presented by overall patients. No formal inferential testing will be performed for either study period. Summaries will be descriptive in nature. All summaries of safety results described in this section will be presented for each study period respectively, unless otherwise noted.

General common rules

All safety analyses will be performed on the safety populations as defined in [Section 2.3.2](#), unless otherwise specified, using the following common rules:

- Safety data in patients who do not belong to the safety population (eg, exposed but not randomized) will be listed separately.
- The baseline value, for both parallel arms and single arm periods, is defined as the last available value obtained up to the date and time of the first IMP administration.
- The PCSA values are defined as abnormal values considered medically important by the Sponsor according to predefined criteria/thresholds based on literature review and defined by the Sponsor for clinical laboratory tests, vital signs, and electrocardiogram (PCSA version dated May 2014 [[Appendix A](#)]). In case the PCSA threshold is within the normal laboratory ranges, the analysis will be done using “<Low Limit Normal” or “>ULN” threshold instead of “<PCSA threshold” or “>PCSA threshold” respectively.
- PCSA criteria will determine which patients had at least 1 PCSA during the TEAE period, taking into account all evaluations performed during the TEAE period, including nonscheduled or repeated evaluations. The treatment-emergent PCSA denominator for a given parameter will be based on the number of patients assessed for that given parameter at least once during the TEAE period.
- All measurements, scheduled or unscheduled, fasting or not fasting, will be assigned to analysis windows defined in [Section 2.5.4](#) in order to provide an assessment for Week 4 to Week 16 time points.

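### By-device laboratory summaries are promised for all parameters, but hematology and biochemistry (20 of 25) have no scheduled post-baseline draw while the two devices run in parallel

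*Protocol*

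**What the plan says.** **The commitment.** Protocol 11.4.4.2: "For laboratory data, including the incidence of PCSAs, actual values and change from baseline will be summarized by treatment group". The same section promises visit-by-visit statistics for all laboratory variables by device group, PCSA counts for each parameter, and shift tables. The synopsis adds: "For vital signs and laboratory parameters, the number of patients with abnormalities and/or potentially clinically significant abnormalities (PCSAs) will be summarized by auto-injector device".

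**Where by-device results exist.** Protocol 11.4 gives results by device for the parallel-arms period and overall for the single-arm period. SAP 2.4.4.2.5 agrees: "The parallel-arm period will be presented by treatment group and the single-arm period will be presented by overall patients". SAP 2.4.4.2.5.3 then covers all laboratory variables, with no exception for hematology or biochemistry.

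**What is drawn.** The flow chart (Protocol 1.2) marks hematology and biochemistry at screening, Day 1 and Week 16. It marks the liver panel and CPK at those visits and also at Weeks 4, 8 and 12. The Visit 6 (Week 4) list in 10.1.4 names only the liver panel and CPK as safety laboratory tests. Table 8 in 9.3 gives "Hematology 2 mL 3 6 mL", that is, 3 hematology samples. Biochemistry also has 3, and CPK and the liver panel have 6 each.

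**Period boundaries.** For patients who continue, Protocol 11.4.4 and SAP 2.1.4.5 end both the TEAE period and the treatment period of the parallel arms on the day before the second injection. For patients who stop, the limits are 70 and 35 days after the first injection.

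**The concern.** The safety objective covers both devices. Protocol 4.2.2 and 9.5 say that the parallel arms allow safety to be compared descriptively up to Week 4. For blood counts, electrolytes, renal markers and glucose, the sampling schedule does not support that comparison. The one scheduled post-baseline value comes at Week 16, when completers have had three SYDNEY doses (AI arm) or four (SYDNEY arm), and it is reported in the pooled single-arm summary.

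Such a table need not come out blank. Unscheduled evaluations count towards PCSAs (Protocol 11.4.4), and the SAP denominator is the patients assessed for that parameter within the TEAE period. Protocol 10.6.2.1 calls for unscheduled hematology and chemistry after certain allergic skin events or worsening injection-site reactions. A by-device percentage could therefore come from a handful of patients, some of them sampled because of an event.

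**Working it through.** The check is a count; no power or sample-size formula applies.

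**1. Reproduce the plan's own figures.** Marks in the flow chart: hematology 3, biochemistry 3, CPK 6, liver panel 6. These match Table 8. Blood volume: 3×2 + 3×2 + 6×2 + 6×1 + 6×3 + 11×5 + 3×5 = 118 mL; with the 5 mL pregnancy sample, 123 mL. Both match Table 8, so the three-sample schedule is not a slip in one table.

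**2. Count parameters (Protocol 9.2.5.2).**

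| Panel | Parameters | Scheduled at Week 4? |
|---|---|---|
| Hematology (RBC, hematocrit, hemoglobin, WBC, 5 differentials, platelets) | 10 | No |
| Biochemistry (Na, K, Cl, Ca, glucose, urea nitrogen, creatinine, albumin, total protein, γGT) | 10 | No |
| Liver panel (AST, ALT, ALP, total bilirubin) | 4 | Yes |
| CPK | 1 | Yes |
| Total | 25 | 5 yes, 20 no |

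Conditional bilirubin fractions are not counted. SAP 2.1.4.5.3 adds derived eGFR, which depends on creatinine; on that list the count is 21 of 26.

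**3. Apply the period cut-off.** Week 4 blood and vital signs are taken at Visit 6, the visit of the second injection. A sample taken that day falls after the stated end of the parallel-arms period. On a literal reading the five Week 4 parameters are lost as well, giving 25 of 25 without a scheduled value for patients who continue, and Week 4 vital signs go with them.

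**4. Who could still contribute hematology or biochemistry?** Protocol 10.3.4 sets a final end-of-study visit 4 weeks after premature discontinuation, and the end-of-study list (10.1.8) includes both panels.
- Number: if all of the assumed 10% drop-out came after dose 1 and split evenly, 0.10 × 33 = 3.3, or about 3 per arm.
- Timing: a patient who stops d days after dose 1 has this visit at about d + 28 days. It is inside the 70-day TEAE window if d ≤ 42, but inside the 35-day treatment period only if d ≤ 7. A patient who stops at Week 4 (d = 28) is sampled at about 56 days, which counts for PCSAs but not for on-treatment quantitative summaries.
- Unscheduled draws after allergic or worsening injection-site events add an unknown, probably small, number.

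**5. Effect of one added draw.** With both panels at Week 4 before dosing, each has 4 samples. Parameters without a scheduled Week 4 value fall from 20 of 25 to 0 of 25. Volume becomes 118 + 2 + 2 = 122 mL, or 123 + 4 = 127 mL.

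**The case against.** The case for the schedule is reasonable. Both arms receive the same 150 mg/mL formulation at the same total dose, and Protocol 4.2.1 calls the regimen established. The documents give no reason to expect blood counts or electrolytes to differ by device after one dose. The objective is to evaluate safety, the comparison is descriptive, and the SAP excludes inferential testing for safety. The yield would be small: with 0 events in 33 patients the Wilson 95% upper bound is 3.84/(33 + 3.84) = 10.4%. A sparse table would show its own small n. All of this stands as a reason not to draw the samples. It does not justify promising by-device tables for every parameter.

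On the cut-off, the intent is probably that Week 4 belongs to the parallel arms, since the parallel-arms mITT definition relies on a Week 4 LDL-C value. But the SAP window table assigns a time point, not a study period, and no sentence overrides the stated boundary.

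Three stronger readings are tempting and are not supported:
- **That these 20 parameters have no post-baseline data.** Week 16 values exist; they belong to the pooled summary.
- **That the by-device tables must contain zero patients, or only patients sampled because of an event.** Early end-of-study visits are planned draws and can fall inside the TEAE window.
- **That the liver panel and CPK are safely comparable by device as written.** They are drawn at the right visit, but the literal cut-off excludes same-day values.

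**Conclusion.** The mismatch is real and narrow. For patients who continue, 20 of 25 listed laboratory parameters have no scheduled post-baseline draw in the only period reported by device. The literal boundary puts the other five, and vital signs, at risk too. The count rests on the flow chart, the visit lists and Table 8, which agree. The figure of about 3 of 33 per arm is an upper illustration: it assumes that the full 10% drop-out follows dose 1, is even across arms, and that every such patient attends the early end-of-study visit within 70 days.

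A reader might infer that the safety evaluation as a whole is undermined. The documents do not support that. Adverse events and injection-site reactions are collected in both arms during the parallel period, and the primary endpoint, sample size, and planned PK and LDL-C comparisons do not depend on these panels. Severity is minor.

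**What to change.** 1. **Correct the boundary for measurements.** State in Protocol 11.4.4 and SAP 2.1.4.5 that every pre-dose Week 4 laboratory and vital-sign value, existing or added, belongs to the parallel-arms period even when taken on the day of the second injection. State in 10.1.4 that the Visit 6 safety bloods and vital signs are taken before dosing; the flow-chart footnotes say this for PK, ADA and lipids but not for the liver panel, CPK or vital signs. The adverse-event cut-off can stay as it is. Cost: wording.

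2. **Then choose one of two.**
   - *Add the draw.* Put hematology and biochemistry on the existing Visit 6 venipuncture, and update the flow chart, 10.1.4 and Table 8 (4 samples each; totals 122 mL, or 127 mL for women of childbearing potential). Cost: 4 mL per patient, the two panels for up to 66 patients, an amendment, and the extra samples in the visiting nurse's supplies, since Visit 6 may be at home.
   - *Narrow the claim.* In the synopsis, Protocol 11.4.4.2 and SAP 2.4.4.2.5.3, limit by-device laboratory summaries to the liver panel and CPK, and say that hematology and biochemistry cannot be compared between devices. Cost: wording. For patients already past Week 4 this is the only option, because the samples cannot be recovered.

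Step 1 is needed with either choice; without it, the narrowed tables could also be nearly empty.
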